4.5.2 Potential Influencing or Confounding Factors and Bias

Known foreseeable factors that could potentially compromise the outcome of the investigation or interpretation of the results or introduce bias into the study are delineated in this section.

One such factor pertains to the participant population that could be enrolled in this investigation. Given the fact that the device could provide an option to receive an AV access for patients who are not candidates for AVF created using traditional surgical methods, could potentially entail a bias towards a population that could be subject to worse outcomes (e.g. an older population, one with more comorbidities, etc.). This potential factor has been mitigated so far as possible with the existing eligibility criteria. This factor could also be counterbalanced by the enrollment of incident participants which are not yet on HD but are in imminent need. These participants may be earlier in their disease progression and may present with comparatively fewer comorbidities than their contemporaries already on HD. Subgroup analyses on endpoints pertaining to participant demographics (e.g. by age group, comorbidities, etc.) may be conducted on any of the pertinent endpoints to explore any differences within the enrolled population.

An additional foreseeable factor pertaining to the patient population would be the potential differences between incident and prevalent participants. Furthermore, within these groups there are potential subgroups that may lend themselves to differences in outcomes. These seven (7) potential subgroups are categorized and defined as detailed in Table 2. To explore any differences in outcomes subgroup analyses may be conducted on the endpoints to explore the characteristics for each group.

Table 2: Participant Status at Time of Index Procedure

Participant Status at Index Procedure		History of Prior Failed AV Access(es)	
Incident	Pre-KRT	Definition: Participants who have not previously and who were not actively receiving any form of KRT	No
Definition: Participants who have not previously and who were not actively receiving HD prior to or at the time of the index procedure but are in need of a	FIC-KKI	prior to the index procedure	Yes
	Pre-HD	Definition: Incident participants who have not	No
vascular access as determined by the referring clinician		previously and who were not actively receiving HD prior to the index procedure	Yes

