Prevalent Definition: Participants who have previously and / or who were actively receiving HD prior to the index procedure	CVC Only	Definition: Prevalent participants who have only	No
		received HD using a CVC prior to the index procedure	Yes
	AV HD Access	Definition: Prevalent participants who have received HD using any form of AV HD access (i e AVG / AVF) prior to the index procedure	Yes

Another potential foreseeable factor pertains to the global nature of this investigation and the varying practice patterns across the regions that may participate. These differences could stem for example from differing surveillance programs, differing criteria for initiating AVF cannulation, among others. This factor is mitigated through CIP stipulated training requirements, as well as maximum enrollment limitations on any single site, and standardization for follow-up interval timing and pertinent requirements. Subgroup analyses between regions may be conducted to explore regional differences for standard of care differences. This could also be expanded to

inter-region subgroup analyses should there be differences in institution types (e.g. public versus private) that participate within a region.

In addition to region and institution type, the training and level of experience with the WavelinQTM EndoAVF system as well as the specialty of the operator could also be a foreseeable factor that could impact the study outcomes. As a mitigation of this factor the training and operator approval requirements delineated in Section 12.2 are implemented. Subgroup analyses looking at the experience level and / or specialty of the operator may also be performed to investigate the impact on results.

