7.3 Sample Size Considerations

The sample size for the study of one-hundred and fifty (150) treated participants was established to assure adequate power for the primary safety and effectiveness endpoints as

well as to result in a sufficient sample size (when accounting for attrition) for assessment of the secondary and exploratory endpoints, specifically for those that only apply to subsets of the overall population (i.e. the incident population and wrist arterial procedure access population).

- 1) *Primary Safety Endpoint* The proportion of participants with freedom from device-or procedure-related SAEs through 30 days (ITT Population).
 - Assumptions:
 - The freedom from device- or procedure-related SAE rate for AVFs created using the WavelinQTM EndoAVF System is estimated at 92.6% through 30 days based on pre-market data;
 - The PG is set at 82.6% using a 10% non-inferiority margin;
 - The rate of attrition through 30 days is assumed to be 10%; and
 - o The Type 1 error is 0.05 (two-sided).
 - Sample Size:
 - A sample size of 150 treated participants [135 evaluable] will give over 92.5% power with a two-sided type I error of 0.05 as calculated using PASS 2019 (One Proportion Exact Test).
- 2) Primary Effectiveness Endpoint Interventions Post Creation to Facilitate AVF Use and / or Maintain AVF Use (Facilitation and / or Maintenance Interventions) through the Timepoint of the 6-Month Follow-Up of the Last Active Treated Participant (AT Population)
 - Assumptions:
 - The number of interventions post creation to facilitate AVF use and / or maintain AVF use after AVF creation using the WavelinQTM EndoAVF System is estimated at 3.0 / PY, a conservative assumption based on pre-market data;
 - The PG is set at 5 / PY to align with the targets and recommendations of the 2019 update of the KDOQI Clinical Practice Guideline for Vascular Access of < 2 interventions to facilitate and < 3 interventions to maintain AVF use;
 - The rate of attrition through 6-, 12-, and 24-months, including lost to followup, death, and other clinical investigation premature withdrawals is assumed to be 20%, 40%, and 60%, respectively; and
 - o The Type 1 error is 0.05 (two-sided).
 - Sample Size:
 - O A sample size of 150 treated participants, yielding more than 100 PY by the time the last active treated participant completes their 6-month follow-up, will give over 99% power with a two-sided type I error of 0.05 as calculated using PASS 2019 (One-Sample Poisson Rate Test).

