7.4.4 Primary Effectiveness Endpoint Hypothesis Test

Objective: To assess if the number of interventions post creation to facilitate AVF use and / or maintain AVF use (Facilitation and / or Maintenance Interventions) per PY for the WavelinQTM EndoAVF System is less than the PG.

The primary effectiveness endpoint will be evaluated by the following hypothesis:

- **H₀:** The number of interventions post creation to facilitate AVF use and / or maintain AVF use (Facilitation and / or Maintenance Interventions) per PY of participants treated with the WavelinQTM EndoAVF System (RwE) is greater than or equal to that of the PG of 5 post creation facilitation and maintenance interventions / PY.
- **H**₁: The number of interventions post creation to facilitate AVF use and / or maintain AVF use (Facilitation and / or Maintenance Interventions) per PY of participants treated with the WavelinQTM EndoAVF System (RwE) is less than that of the PG of 5 post creation facilitation and maintenance interventions / PY.

That is:

 H_0 : RwE \geq 5 post creation facilitation and maintenance interventions / PY

H₁: Rw_E < 5 post creation facilitation and maintenance interventions / PY

Rejection of the null hypothesis will signify that the number of interventions post creation to facilitate AVF use and / or maintain AVF use (Facilitation and / or Maintenance Interventions) per PY of AVFs created using the WavelinQTM EndoAVF System is less than the PG of 5 post creation facilitation and maintenance interventions / PY.

The primary effectiveness analysis will be conducted on the AT population after the last active treated participant completes their 6-month follow-up; by this time, all participants still in the clinical investigation will have at least 6-months of data. The number of Facilitation and / or Maintenance Interventions per PY will be estimated by Poisson regression model with only the intercept term, and the estimate and 95% CI will be provided, and the p-value comparing to the PG will be calculated by a chi-square test.

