7.7.3 Handling of Missing Data

Investigation endpoints may have missing data due to a participant's withdrawal of consent, the withdrawal of a participant by the PI, a participant loss to follow-up and the death of a participant. Data may also be missing from investigation endpoints due to deviations and / or missing data collection. It is important to minimize missing data by all means and to always record the reason for omission.

For the primary safety endpoint, a conservative approach will be used for the handling of missing data: If a participant has a specified event (device-related or procedure-related SAE), the participant will be included irrespective of if the participant prematurely discontinues prior to the 30 day timepoint; if a participant prematurely discontinues before 30 days without the occurrence of a specified event, the participant will be considered not evaluable and will not be included in the primary safety endpoint analysis.

For the primary effectiveness endpoint, the Poisson regression model will be used to analyze the data. In the Poisson regression model, missing data handling is a standard part of the analysis: If a treated participant prematurely discontinues prior to the data cut, that participant's study duration will be considered as the period of time between the index procedure and their premature discontinuation, and the corresponding number of facilitation and/or maintenance interventions in that specific duration will be used for analysis.

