    - O A sample size of 150 treated participants, yielding more than 100 PY by the time the last active treated participant completes their 6-month follow-up, will give over 99% power with a two-sided type I error of 0.05 as calculated using PASS 2019 (One-Sample Poisson Rate Test).

Hence, the sample size of 150 treated participants will provide approximately 92.5%\*99%= 91.5% power for the co-primary endpoints.

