#### 5.1.2 Primary Effectiveness Endpoint

The primary effectiveness endpoint of the clinical investigation is an effectiveness measure based on the number of interventions post creation to facilitate AVF use and / or maintain AVF use through the timepoint of the 6-month follow-up of the last active treated participant.

The primary effectiveness endpoint will be evaluated by the following hypothesis:

- H0: The number of interventions post creation to facilitate AVF use and / or maintain AVF use (Facilitation and / or Maintenance Interventions) per patient year (PY) of participants treated with the WavelinQTM EndoAVF System (RWE) is greater than or equal to that of the PG of 5 post creation facilitation and maintenance interventions / PY.
- H1: The number of interventions post creation to facilitate AVF use and / or maintain AVF use (Facilitation and / or Maintenance Interventions) per PY of participants treated with the WavelinQTM EndoAVF System (RWE) is less than that of the PG of 5 post creation facilitation and maintenance interventions / PY.

That is:

 $H_0$ : RWE  $\geq$  5 post creation facilitation and maintenance interventions / PY

H1: RWE < 5 post creation facilitation and maintenance interventions / PY

Rejection of the null hypothesis will signify that the number of interventions post creation to facilitate AVF use and / or maintain AVF use (Facilitation and / or Maintenance Interventions) per PY of AVFs created using the WavelinQTM EndoAVF System is less than the PG of 5 post creation facilitation and maintenance interventions / PY.

Facilitation and/ or maintenance intervention will be identified if:

On the Post-Procedure Intervention page, Date of Post Procedure Intervention is not NULL and before or on the cutoff date of the database lock, and Type of Intervention is checked as Facilitation and/ or Maintenance. Note in the event that there are multiple treatments performed during the same procedure driven by multiple reasons, each reason driving the intervention will be counted as a separate intervention.

For each participant, the number of interventions post creation to facilitate AVF use and / or maintain AVF use through the timepoint of the 6-month follow-up of the last active treated participant is expressed as:

(Number of observed facilitation and/or maintenance interventions \* 365) / Length of investigation duration (Days)

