Length of investigation duration (Days) is from the date of index procedure to the cutoff date of database lock (cutoff date – date of index procedure +1). If a participant discontinued early, then the last date of available study data (including the unscheduled visit date) will be used to calculate the length of investigation duration (last date of

available study data – date of index procedure +1). If a participant's endoAVF has permanent abandonment the date of permanent abandonment will be used to calculate the length of investigation duration (permanent abandonment date – date of index procedure +1).

The primary effectiveness analysis will be conducted on the AT population after the last active treated participant completes their 6-month follow-up; by this time, all participants still in the clinical investigation will have at least 6-months of data. The number of Facilitation and / or Maintenance Interventions per PY will be estimated by Poisson regression model with only the intercept term, and the estimate and 95% CI will be provided using the Wald method, and the p-value comparing to the PG will be calculated by a Chi-square test. The analysis will be repeated on the PP population.

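### The co-primary effectiveness test uses a plain intercept-only Poisson model with no allowance for overdispersion; if interventions cluster within participants, the 95% CI is too narrow and the 0.05 error is not held

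*SAP*

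**What the plan says.** Protocol 7.4.4 states that the facilitation and maintenance intervention rate "will be estimated by Poisson regression model with only the intercept term", with a chi-square p-value against the performance goal of 5/PY. SAP 5.1.2 keeps this and adds the Wald interval: "estimated by Poisson regression model with only the intercept term, and the estimate and 95% CI will be provided using the Wald method". The only repeat of the analysis in that section applies the same model to the per-protocol population. The sample size rests on the same variance assumption, "as calculated using PASS 2019 (One-Sample Poisson Rate Test", with a planning rate that "is estimated at 3.0 / PY, a conservative assumption based on pre-market data".

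Three further provisions bear on the point:
- **Counting.** SAP 5.1.2 states that when one procedure has several reasons, "each reason driving the intervention will be counted as a separate intervention".
- **Heterogeneity.** Protocol 4.5.2 says: "An additional foreseeable factor pertaining to the patient population would be the potential differences between incident and prevalent participants". It adds: "Another potential foreseeable factor pertains to the global nature of this investigation and the varying practice patterns across the regions that may participate".
- **Exposure.** For early discontinuation, Protocol 7.7.3 cuts follow-up at discontinuation and "the corresponding number of facilitation and/or maintenance interventions in that specific duration will be used for analysis".

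**The concern.** An intercept-only Poisson model gives every participant the same rate and treats events as independent. Its standard error for the log rate is 1/√(total events), which is right only if the variance of the count equals its mean. Repeat events alone do not break this, since a Poisson count allows repeats. Unequal rates between participants do break it, and so do events that arrive together. The protocol expects the first (incident versus prevalent status, regional practice), and the per-reason rule creates the second. No term in the model or its variance absorbs either.

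If overdispersion is present, the standard error is too small, the interval too narrow, and the test declares the rate below 5/PY too often when it is not. This is the formal test and headline interval of a co-primary endpoint, and SAP 5.3.6 uses the same method for the exploratory intervention rates.

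A smaller point: SAP 5.1.2 gives a per-participant annualised value and does not state the model response or offset. Protocol 7.7.3 and the PY-based sizing point to count plus exposure, so this only needs stating. SAP Appendix 2, listed by title only, may already do so.

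**Working it through.** **1. The plan's own power figure.** Inputs (Protocol 7.3, SAP 2.4): rate 3.0/PY, goal 5/PY, 100 PY, two-sided 0.05. Expected events at 3.0/PY are 300. Wald power = Φ(|ln(3/5)|·√300 − 1.96) = Φ(8.85 − 1.96), above 99.99%. The exact test rejects at 456 or fewer events (456/100 = 4.56/PY; size 0.0246), also with power above 99.99%. The stated figure of over 99% reproduces under its own Poisson assumption.

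**2. Exposure.** Uniform accrual over 18 months (Protocol 3), data cut at month 24, and attrition interpolated through 20/40/60% at 6/12/24 months give about 138 PY for 150 participants. This agrees with the plan's figure of more than 100 PY.

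**3. Variance ratio.** Let participant i have follow-up fᵢ and a rate equal to r times a gamma frailty with mean 1 and variance k. The variance of the total count, divided by its Poisson variance, is

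V = 1 + k·r·(Σfᵢ²/Σfᵢ), with Σfᵢ²/Σfᵢ ≈ 1.20 years in this design.

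The true standard error is √V times the Poisson one. False success at 5/PY is then approximately Φ(−1.96/√V). For k = 0.5: V = 1 + 0.5·5·1.20 = 4.0, and Φ(−0.98) = 16.4%.

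**4. Simulation.** 10,000 trials per cell, 150 participants, design as in step 2. Plain test: z = ln(rate/5)·√events. Robust standard error: √[n/(n−1)·Σ(yᵢ − rate·fᵢ)²]/events. The values of k are assumptions. The two-sided error column comes from 4,000 trials per cell.

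| k | V at 5/PY | False success at 5/PY, plain (nominal 2.5%) | Same, robust | Two-sided error at 5/PY, plain | 95% CI coverage at 3/PY, plain | Decisions differ at 4/PY |
|---|---|---|---|---|---|---|
| 0 | 1.0 | 2.7% | 2.8% | 5.3% | 95% | 0% |
| 0.25 | 2.5 | 10.5% | 2.9% | 21% | 85% | 4% |
| 0.5 | 4.0 | 16.8% | 3.1% | 32% | 76% | 15% |
| 1 | 7.0 | 23.8% | 3.3% | 45% | 64% | 31% |
| 2 | 13.0 | 30.1% | 3.9% | 58% | 51% | 47% |

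Robust coverage at 3/PY is 94–95% throughout. At 3/PY the two methods reach the same decision in about 99.9% of trials or more up to k = 1, and in about 96% at k = 2.

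**5. Highest observed rate that passes.** Solve ln(r/5) = −1.96·√(V/(138·r)). With V = 1, r = 4.63/PY. With V fixed at 2, 4 and 6, r = 4.47, 4.25 and 4.08/PY. If V instead follows step 3 at the observed rate, k = 0.25, 0.5, 1 and 2 give 4.43, 4.29, 4.09 and 3.81/PY.

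**6. Per-reason counting alone.** If a fraction q of procedures carries two reasons (assumed), V = (1 + 3q)/(1 + q). For q = 10%, 20% and 30%, V = 1.18, 1.33 and 1.46. Simulated false success, with the counted rate held at 5/PY, is 3.4%, 4.2% and 5.0%. This source is minor next to unequal participant rates.

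**7. Exposure ended at abandonment (SAP 5.1.2).** Calibrated to the 77.3% six-month cumulative patency in Protocol 2.1.2, with abandonment independent of the intervention rate (assumption), exposure is about 115 PY. Plain false success for k = 0.25 to 2 is 9.9%, 15.5%, 22.9% and 30.0%; robust is 3.0–4.4%.

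**The case against.** The strongest reply is that the decision zone may be remote. The error figures apply at a true rate of exactly 5/PY, while the plan assumes 3.0/PY and calls that conservative. Protocol 2.1.2 reports 72.4% six-month primary patency; under a constant hazard that is −ln(0.724)/0.5 ≈ 0.65 first events per PY. The interval error also shrinks with the rate: at 1/PY, coverage over the same range of k is about 91%, 88%, 82% and 72%. This stands as a limit on how often pass/fail would change. It does not rescue the interval or the error rate at the null. The patency figure also cuts both ways: a homogeneous 3.0/PY would leave only exp(−1.5) ≈ 22% of participants intervention-free at six months. Either the true rate is well below 3.0 or interventions concentrate in a minority. Definitions in the prior studies may differ, so this is indicative only.

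Other points that stand in part:
- No dispersion value is given, so every inflation figure is conditional. That is also the reason to choose a variance that does not depend on one.
- Per-reason counting raises the observed rate, which works against success. It does not correct the standard error.
- Protocol 7.7.2 and SAP 5.1.3 plan poolability analyses by region or site, and subgroup analyses are allowed. These look at heterogeneity but leave the primary standard error unchanged.
- A participant-level sandwich does not cover correlation shared within a site or region, and it is slightly liberal at k = 2 (3.9–4.4% against 2.5%).
- The SAP appendices are listed by title only. No title suggests a dispersion rule, but their content cannot be checked.

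**Conclusion.** The concern holds as a conditional statement: if interventions cluster within participants, the planned test does not hold its 0.05 error and the planned 95% CI under-covers. The omission is certain in the supplied text. The size is not, because it rests on an assumed frailty variance of 0.25 to 2. Over that range, false success at 5/PY is 10.5% to 30.1% against 2.5%, and coverage at 3/PY is 85% to 51%.

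This is not a power error. At the planned 3/PY the trial would nearly always pass by either method. The decision depends on the method mainly when the observed rate lies between about 3.8 and 4.6/PY; the reported interval is affected at any rate, less so at low rates. It should be fixed before database lock, since a variance method chosen after seeing the data would be open to challenge.

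**What to change.** In SAP 5.1.2, and for the intervals in SAP 5.3.6:
- Pre-specify one primary method: an intercept-only Poisson model of each participant's raw count with log(person-years) as offset. Take the 95% CI and the chi-square test of log(rate) against log(5) from a participant-level robust (sandwich) variance.
- Report the dispersion estimate.
- Keep the plain Poisson model or a negative binomial model as sensitivity analysis only.
- State that the annualised per-participant value is descriptive and not the model response, consistent with Protocol 7.7.3.
- Acknowledge that correlation within sites is not covered by this variance.

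Protocol 7.4.4 names the Poisson model and a chi-square test but no variance estimator, so the change is compatible with it. The cost is SAP wording and one or two lines of SAS, with a wider interval if clustering exists: at 3/PY and k = 1 the mean upper limit moves from 3.30 to 3.68/PY. Robust power at 3/PY is 99.9% at k = 1 and 95.6% at k = 2 (99.6% and 93.5% if exposure also stops at abandonment), so no extra participants are needed. With no heterogeneity the robust test costs almost nothing (false success 2.8% against 2.7%).

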### **5.1.3** Poolability of Investigational Sites

The primary endpoints will be summarized by. Sites with fewer than 10 treated participants will be pooled by site number to form combined sites with at least 10 participants. For the primary safety endpoint, logistic regression will be used to estimate; for the primary effective endpoint, Poisson regression will be used.

